### 6.2.3.2 Supportive Analysis of the Primary Efficacy Variables

A tipping point analysis will be performed as the sensitivity analysis under missing not at random (MNAR) assumption. Based on the primary analysis model, we will vary assumptions about the missing outcomes to assess how severe departures from the control-based imputation model it can be to overturn the statistical significance conclusions. The procedure will impute the missing data with observations only from placebo arm, and adjust the imputed values for observations in the vericiguat treatment arm for a specified sequence of shift parameters. Multiple imputation will be done using SAS PROC MI under missing not at random (MNAR) assumption (Appendix 9.2).

Also, the same primary efficacy model will be repeated on PEAS (Section 5.1.4) as a supportive efficacy analysis.

In addition, the primary analysis model will be applied to all assessments post-baseline prior to study treatment discontinuation on FAS and PPS.

Furthermore, the same primary analysis model will be repeated under missing at random (MAR) assumption, which means no missing data imputations will be performed.

### 6.2.4 Secondary efficacy variable

The secondary endpoint is change from baseline in the 6 MWT at 24 weeks. The estimand of interest is the de facto or treatment policy estimand.

Population: Defined through study inclusion/exclusion criteria (see protocol Section 6.1 and 6.2).

Variable: Change from baseline in 6 MWT from baseline to Week 24.

Approach of intervention effect: Regardless of stopping study treatment or adherence to study treatment.

Summary measure: Difference of LS means at Week 24.

[figure not shown]
The secondary endpoint will be analyzed in the same manner as the primary endpoint and on the KCCQ (6MWT) (Section 5.1.3). Missing data will be imputed based on a pattern-mixture model with control-based pattern imputation (Appendix 9.1). For those patients who had died during the study, a score of 0 will be assumed from the time of death onward.

A supportive analysis will be repeated using the MMRM model without any missing data imputations. Also, the same model will be applied to all assessments post-baseline prior to study treatment termination.

### 6.2.5 Multiplicity adjustment

The study uses the graphical method of Maurer and Bretz [22] to provide strong multiplicity control across the primary KCCQ PLS hypotheses and the secondary 6 MWT hypotheses. The overall two-sided alpha level will be controlled at 0.05. The two primary hypotheses will be tested using the Bonferroni procedure, each at a splitted level of alpha 0.025. The two secondary hypotheses will be tested based on a parallel gatekeeping principle. As shown in Figure 6-1, if the test of both primary and secondary endpoints at one of the dose groups is significant at the alpha level of 0.025, the primary and secondary endpoint at the other dose group can be tested at the alpha level of 0.05, in an ordered manner. Figure 6-1 shows the  $\alpha$ -allocation for each hypothesis in the circle representing the hypothesis.

**Figure 6-1  $\alpha$ -allocation for the primary and secondary hypotheses**

Overall, the primary analysis will be claimed to have a positive outcome if the null hypothesis for at least one of the two primary hypotheses can be rejected.

## 6.2.6 Other KCCQ domains

Change from baseline in other KCCQ domains (Symptom Frequency, Symptom Burden, Social limitation, Quality of Life), KCCQ summary scores (TSS, CSS and OSS) will be summarized by visit. Cumulative distribution functions will be plotted to compare the proportion of patients who are meeting certain thresholds from vericiguat and placebo arms. The variables will be analyzed using the MMRM model with no missing data imputation. The proportion of patients with changes from baseline by >5 points at 24 weeks and other thresholds (e.g. >3, >7, >10, >15, >20) in the other KCCQ domains as well as OSS, CSS, TSS and SFS will be summarized. The proportion of patients with decline from baseline by >5 points at 24 weeks, as well as other thresholds (e.g. >3, >7, >10, >15, >20) in the other KCCQ domains and summary scores will also be summarized.

## 6.2.7 EQ-5D-5L

Frequencies of answers to individual questions will be displayed by treatment group and overall by visit. In addition, changes from baseline for the single questions will be classified into the following categories: Improvement by two or greater Likert points, Improvement by one Likert point, No change, Worsening by one Likert point, Worsening by two or greater Likert points. Frequencies of the different categories will be displayed by assigned treatment group and overall by visit.

The EQ-5D Visual Analogue Scale (VAS), the preference weighted summary score and the corresponding changes from baseline will be described by treatment group and visit.

The summary scores of EQ-5D-5L (UK and US) as well as the EQ Visual Analogue Scale (VAS) and the corresponding changes from baseline will be described by treatment group and visit.

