9.4.8 Six-minute walk test

The 6MWT is designed to evaluate a patient's exercise capacity while performing an everyday activity (32). During this study, a 6MWT including Borg CR 10 Scale will be conducted at different time points as specified in Section 9.2, for further details on assessment refer to Section 16.1. A familiarization 6MWT will be performed during the run-in phase. To avoid any interactions, it is not permitted to perform the familiarization test on the same day as the baseline 6MWT.

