Other continuous variables including change from baseline to week 24 in other KCCQ domains, EQ-5D-5L, fried frailty score and NT-proBNP, will be analyzed using the MMRM

[figure not shown]
model. For categorical variables such as NYHA class, PGIC, PGIS, the relative response level change will be summarized by each visit. Incidences of cardiovascular death and total heart failure hospitalizations, as well as all-cause mortality and CV hospitalizations, MI and stroke will be summarized. Kaplan Meier curves of the composite endpoints (see Section 9.4) will be presented.

Details on any descriptive subgroup analyses will be specified in the SAP. These will include region, gender, atrial fibrillation status, patient randomization time (before or after discharge from HF hospitalization, or post IV diuretic treatment without hospitalization), and the time from HF hospitalization or IV diuretic treatment to randomization (<3 month vs. ≥ 3 month).

Multiplicity adjustment:

The study uses the graphical method of Maurer and Bretz (33) to provide strong multiplicity control across the primary KCCQ PLS hypotheses and the secondary 6 MWT hypotheses. The overall two sided alpha level will be controlled at 0.05. The two primary hypotheses will be tested using Bonferroni procedure, each at a splitted level of alpha 0.025. The two secondary hypotheses will be tested based on parallel gatekeeping principle. If both primary hypotheses can be rejected, the secondary family will be tested at a full alpha level 0.05 (two sided). If only one primary hypothesis is shown to be statistically significant, then only the secondary hypothesis based on the same dose group can be tested at an alpha level carried forward from the primary family testing, i.e., 0.025 (two sided). In this case, if the secondary hypothesis is rejected, the alpha spending associated with this dose group (0.025) will be re-utilized to test the other failed primary hypothesis again. Figure 10-1 shows the α -allocation for each hypothesis in the ellipse representing the hypothesis.

Figure 10-1 α -allocation for each hypothesis in the ellipse representing the hypothesis

Overall, the primary analysis will be claimed to have a positive outcome if the null hypothesis for at least one of the two primary hypotheses can be rejected.

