## Other objectives:

- To evaluate the efficacy of vericiguat 10 mg and the efficacy of vericiguat 15 mg in comparison to placebo on improving:
  - Symptom frequency as measured by the KCCQ SFS
  - Perceived exertion experienced by patients during 6MWT as measured by Borg CR 10.
  - Other patient-reported outcomes such as the generic health-related quality of life measure EQ-5D-5L and the Fried-based frailty score
  - NYHA class
  - Laboratory variables such as NT-proBNP from baseline to 24 weeks
- To collect and summarize death including cardiovascular death and CV hospitalizations including heart failure hospitalizations, MI and stroke, and outpatient HF events.
- To create the cumulative distribution function of KCCQ PLS, OSS, CSS, TSS and SFS change from baseline to 24 weeks.
- To evaluate PK of vericiguat in patients with HFpEF, and
- To evaluate the concentration-QTc relationship of vericiguat at the 15 mg dose level.
- Optional pharmacogenetic research: To explore the relationship between genetic variation and clinical characteristics of patients, independent and dependent of the treatment administered. Variations across the human genome may be analyzed for association with clinical data collected in this study.
- To evaluate further biomarkers to investigate the drug (i.e. mode-of-action-related effect and / or safety) and / or the mechanisms of the disease

- Optional accelerometry substudy: to collect exploratory data by activity tracking

**Note:** Analyses for PK, biomarker, and optional objectives (including accelerometry) will be specified in a separate supplementary SAP.

[figure not shown]

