#### **7.1.1     Changes from the protocol**

None

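### The SAP reduces the protocol's EQ-5D-5L and Fried frailty MMRM to by-arm description while declaring no change from the protocol

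*SAP*

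**What the plan says.** Protocol 10.3.1, under other efficacy variables, states that continuous variables, including change to week 24 "in other KCCQ domains, EQ-5D-5L, fried frailty score and NT-proBNP, will be analyzed using the MMRM".

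SAP 6.2.7 tabulates EQ-5D-5L item responses and categories of change, and then says: "The EQ-5D Visual Analogue Scale (VAS), the preference weighted summary score and the corresponding changes from baseline will be described by treatment group and visit". A second paragraph largely repeats this with a different definition of the index: "The summary scores of EQ-5D-5L (UK and US) as well as the EQ Visual Analogue Scale (VAS) and the corresponding changes from baseline will be" summarised in the same way. SAP 6.2.8 gives response frequencies for the Fried questions and the proportions with one or more and with three or more frailty characteristics. Neither section contains a model, a treatment difference or an interval.

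For the other KCCQ domains and summary scores, SAP 6.2.6 keeps the protocol's method: "The variables will be analyzed using the MMRM model with no missing data imputation".

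SAP 7.1.1 has the title "Changes from the protocol" and its whole entry is the word None.

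Borg CR10 is an objective against placebo in protocol section 4 and SAP section 2: "Perceived exertion experienced by patients during 6MWT as measured by Borg CR 10". It is collected with the walk test (protocol 9.4.8: "During this study, a 6MWT including Borg CR 10 Scale will be conducted at different time points as specified in Section 9.2"). No analysis section of the SAP names it.

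**The concern.** A reader who relies on SAP 7.1.1 would take the planned EQ-5D-5L and Fried analyses to be those of the protocol. They are not.

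For EQ-5D-5L the loss has some substance. Protocol section 5 supports the choice of KCCQ PLS as primary endpoint partly by the EQ-5D-5L improvement that accompanied it in the earlier phase IIb trial. Whether that pattern recurs here is a natural question. The direct answer is an adjusted difference from placebo with an interval, placed beside the KCCQ PLS result. The protocol planned such an estimate and the SAP does not. If one is wanted after unblinding, its model, covariates and value set would then be chosen with the data in view.

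**Working it through.** The documents give no effect size, SD or power for EQ-5D-5L, Fried or Borg, so there is no figure to reproduce. The check is a comparison of text.

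| Measure | Protocol 10.3.1 | SAP | Declared in SAP 7.1.1 |
|---|---|---|---|
| Other KCCQ domains | MMRM | MMRM, no imputation (6.2.6) | Nothing to declare on use of the model |
| EQ-5D-5L | MMRM | By-arm description (6.2.7) | No |
| Fried frailty score | MMRM | Frequencies and proportions (6.2.8) | No |
| NT-proBNP | MMRM | Biomarker analyses deferred to a supplementary SAP (section 2) | Not counted here |
| Borg CR10 | None named | None named; general rule of 4.1 only | Nothing to declare |

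**Does the SAP explain the change elsewhere?** SAP section 2 says that objectives beyond the primary and secondary hypotheses are listed for description. That does not account for it. KCCQ symptom frequency stands in the same list of other objectives as EQ-5D-5L, and SAP 6.2.6 keeps an MMRM for it. SAP 4.1 applies descriptive statistics to every variable, including those that also have a model, so it does not replace one. The note on the supplementary SAP covers PK, biomarker and optional objectives and names neither EQ-5D-5L nor Fried.

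**What is not produced.** Two EQ-5D-5L measures (VAS and index) times two doses against placebo gives 2 × 2 = 4 week-24 contrasts, each without a planned adjusted estimate or interval.

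**Is the model feasible?** SAP 6.2.1 schedules EQ-5D-5L at baseline and weeks 2, 6, 12, 18 and 24, the same visits as KCCQ. The structure in SAP 6.2.3.1 therefore carries over with the baseline covariate exchanged. Fried differs: SAP 6.2.2 schedules it at baseline and week 24, plus premature discontinuation. With one scheduled post-baseline visit there is little for a repeated-measures model to use, so recording the change is a sensible remedy there.

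**Which index?** SAP 6.2.1 derives the summary score from US general-population weights. SAP 6.2.7 reports UK and US scores, and no UK value set is cited. With both descriptive this is loose wording, but a model needs one named set.

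**Borg.** SAP 6.2.4 assigns a walk distance of 0 from death onward. In protocol Appendix 2, a Borg rating of 0 means no exertion at all, the most favourable value. Carrying the walk-test rule over to Borg would score a death as the best outcome.

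**The case against.** The strongest reply is that these are exploratory measures that the SAP calls descriptive. They lie outside the multiplicity scheme of SAP 6.2.5, which covers only KCCQ PLS and 6MWT. Means, SDs and missing counts by arm and visit, placebo included, show whether EQ-5D-5L moves in the same direction as KCCQ PLS. All of that stands, and it limits the weight of the point. It does not remove the mismatch with the protocol or the inaccurate entry in SAP 7.1.1.

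A reader might infer several stronger things that the documents do not support:

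- That the EQ-5D-5L and Borg objectives cannot be answered. By-arm summaries allow a crude comparison; what is missing is an adjusted estimate and its precision.
- That EQ-5D-5L was singled out. The Fried model was dropped in the same way.
- That the Borg gap breaks a protocol commitment. Protocol 10.3.1 names no Borg analysis, protocol 9.4 does not list Borg among the efficacy variables, and SAP 4.1 implies a default summary. A Borg model would be a new request, on a scale that allows ratings above 10 and with no rule for patients who die or cannot walk.
- That the loss of precision can be quantified. The documents give no correlation between baseline and change for EQ-5D-5L, so any figure would be assumption.

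**Conclusion.** The point holds as an undeclared departure from the protocol. The MMRM planned for EQ-5D-5L and Fried has become by-arm description, and SAP 7.1.1 says nothing changed. The practical effect is four missing adjusted week-24 contrasts for EQ-5D-5L, a missing Fried model, and an index with two descriptions. No error rate, power figure or confirmatory conclusion is touched, so it is a worthwhile correction and not a serious flaw. This rests on the SAP text alone and assumes that no supplementary plan restores the EQ-5D-5L or Fried model; the SAP's note on its supplement mentions neither. The Borg CR10 gap is real but secondary, and the conclusion does not depend on it.

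**What to change.** 1. In SAP 6.2.7, restore the MMRM for change from baseline in EQ VAS and in the EQ-5D-5L index. Include baseline value, region, heart rhythm, treatment, visit and treatment-by-visit, with no imputation, as in SAP 6.2.6. Report each dose against placebo at week 24 with a nominal confidence interval.
2. Name one value set for the modelled index, the US set of SAP 6.2.1, and label the other as descriptive with its source. Merge the two overlapping paragraphs of SAP 6.2.7.
3. In SAP 7.1.1, replace the present entry with the Fried change and its reason. If the EQ-5D-5L model is not restored, list that change there too.
4. Add a sentence on Borg CR10 saying which visits are summarised and how patients without a walk test are handled, and stating that the 6MWT zero-at-death rule does not apply.

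The cost is SAP wording before unblinding and reuse of the existing model code on data already collected at the KCCQ visits. No new assessment is needed.

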## 6.2.8 Fried frailty score

Frequencies of patients with each response option for each question will be presented by treatment group and overall by visit. Proportions of patients with one or more responses characteristic of frailty and those with three or more characteristics will be summarized.

## 6.2.9 Clinical outcome events

All patients will be followed until study completion to assess for vital status. Potential pre-specified clinical outcome events will be submitted for adjudication to an independent CEC. The following events will be collected and analyzed to explore the efficacy of study drug treatments on clinical outcomes:

- All deaths (CV and non-CV, including outpatient death)
- CV hospitalizations including HF and non-HF hospitalizations (i.e. myocardial infarction and stroke)
- Outpatient HF events, such as IV diuretic use for HF or urgent HF visits

Incidence of events, including all deaths, CV deaths and non-CV deaths, total CV hospitalizations, HF hospitalizations, non-HF hospitalizations (i.e. myocardial infarction and

stroke), as well as outpatient HF events will be summarized. Patients without an event will be censored at their last contact date (the latest date among all known assessments or follow-up dates).

In addition, Kaplan Meier curves of the composite endpoints will be presented by treatment:

- Time to first occurrence of the composite of CV death or heart failure hospitalization.
- Time to first occurrence of the composite of CV death, HF hospitalization, worsening from baseline in NYHA class, or worsening from baseline in PGIC
- Time to first occurrence of the composite of CV death, heart failure hospitalization, worsening from baseline in NYHA class, or worsening from baseline in KCCQ CSS

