If permanent discontinuation of study drug treatment becomes necessary due to intolerance even at the lowest dose step or any other reason, this does not mean that the patient has withdrawn from the study follow-up. Participants may be allowed to begin study treatment again if deemed medically appropriate, unless the participant's treatment assignment has been unblinded by the investigator/delegate and/or non-study treating physician.

For participants who are discontinued from study treatment but continue to be monitored in the study, all visits and procedures, as outlined in the schedule of assessments, should be completed. If the patient is unable to attend scheduled study visits, follow-up of clinical events specified as exploratory endpoints may continue by phone, unless the patient explicitly withdraws his/her consent to any type of follow-up.

Withdrawal criteria

Patients *must* be withdrawn from the **study drug**, while all efforts should be made to continue all protocol procedures also upon study drug discontinuation, if any of the following occurs:

- In case of pregnancy or breastfeeding.
- If the investigator believes that for safety reasons (i.e., adverse event) it is in the best interest of the subject to stop study drug even at the lowest dose.

Patients *may* be withdrawn from the **study drug** if any of the following occurs:

- If a significant violation of the protocol occurs, as defined by the sponsor and the coordinating investigator.
- If the randomization code is broken via IxRS.

Patients *must* be withdrawn from the **study** if any of the following occurs:

- At their own request; at any time during the study and without giving reasons, a patient may decline to participate further. The patient will not suffer any disadvantage as a result.

Patients *may* be withdrawn from the **study** if any of the following occurs:

- If, in the investigator's opinion, continuation of the study would be harmful to the patient's well-being.
- At the specific request of the sponsor and in liaison with the investigator (e.g., obvious non-compliance, safety concerns).

Depending on the time point of withdrawal, a withdrawn patient is referred to as either "screening failure" or "dropout" as specified below:

Screening failure

A patient who, for any reason (e.g. failure to satisfy the selection criteria), terminates the study before the time point used for the definition of "dropout" (see below) is regarded a "screening failure".

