9.1 Tabular schedule of evaluations

Table 9-1: Tabular schedule of assessments

Trial Periods	Screening ^a	Base-line	Titration / Sham titration		Treatment			End of treatment	Safety Follow-Up ^b	Premature Treatment Discontinuation	
			3	4	5	6	7			11	12
Visit Number	1	2						9	10		
Week			2	4	6	8	12	18	24	28	
Visit Window (Days)	-28-1	1	14±3	28±3	42±3	56±3	84±3	126±3	168±3	196±7	At time of permanent treatment discon 28±7 days after last dose
• Informed consent main study	•										
• Demographic data											
• Medical and surgical history											
Optional - Informed consent for pharmacogenetic research	• ^c										
Optional - Informed consent for accelerometry	•										
Concomitant medication	•	•	•	•	•	•	•	•	•	•	•
Inclusion / exclusion criteria	•	•									
Urine pregnancy test (local) ^g	•	•				•					
Randomization (IxRS)		•									
ePRO: KCCQ, PGIC ^d , PGIS, EQ-5D-5L		•	•	•	•	•	•	•	• ^e	•	• ^e
Fried Frailty score		•							•		•
NYHA class	•	•	•	•	•	•	•	•	•	•	•
Blood pressure, pulse rate ^f	•	•	•	•	•	•	•	•	•	•	•
ECG		• ^g						• ^h			• ⁱ
Only in patients eligible for PK/QT assessment ^j	ECG	• ⁱ		• ⁱ				• ⁱ			
	PK sample predose				•			•			
	PK sample 1-2 h, and 3-6h post	• ^k		•				•			
6 MWT	•	•				•		•	•	•	•
Local lab blood sample ^l	•										
Central lab blood sample ^m		•			•			• ^s			•
Optional pharmacogenetic research blood sample		• ^c									
Physical exam, weight, height ⁿ	•	•	•	•	•	•	•	•	•	•	•
Adverse events	•	•	•	•	•	•	•	•	•	•	•
Drug accountability ^o			•	•	•	•	•	•			•
Dispense study drug		•	•	•	•	•	•	•			
Optional uptitration ^p						• ^t	• ^u	• ^t	• ^u		
Optional accelerometry	• ^t	• ^u				• ^t	• ^u	• ^t	• ^u		

Footnotes:

- a. Can start as early as at time of hospitalization or IV diuretic treatment for HF or up to 6 months after. Should start no more than 4 weeks before randomization. Screening visit and baseline visit can take place on the same day.
- b. In case of premature discontinuation of study treatment, vital status will be collected at week 28 by any method (e.g. via telephone call or e-mail), unless the patient has specifically withdrawn consent for further study follow-up.
- c. Optional pharmacogenetic informed consent and blood collection may also be performed at a later visit. Blood sample for genetic analysis will only be taken if the patient signed the separate consent for the pharmacogenetic research study.
- d. Not performed at baseline visit.
- e. Only KCCQ and EQ-5D-5L performed at visit 10 and 12.

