9.2.10 Visit 10 Safety follow-up – Day 196±7

- KCCQ and EQ-5D-5L (see Section 9.4)
- Assessment of NYHA class
- Adverse events (see Section 9.6.1)
- Physical examination incl. weight
- Vital signs (BP and HR). See Section 9.7.5.
- 6MWT
- Vital status will be collected for all randomized patients, including those who did not attend the visit or were permanently discontinued, by any method (e.g. via telephone call or e-mail), unless the patient has specifically withdrawn consent for further study follow-up.

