#### **Assessment of NYHA class**

NYHA class will be assessed according to the classification below:

- Class I: No limitation of physical activity
- Class II: Slight limitation of physical activity in which ordinary physical activity leads to fatigue, palpitation, dyspnea, or anginal pain; the person is comfortable at rest
- Class III: Marked limitation of physical activity in which less-than-ordinary activity results in fatigue, palpitation, dyspnea, or anginal pain; the person is comfortable at rest
- Class IV: Inability to carry on any physical activity without discomfort but also symptoms of heart failure or the anginal syndrome even at rest, with increased discomfort if any physical activity is undertaken

The NYHA class will be completed at baseline and all following visits.

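### One last-contact censoring rule leaves patients at risk in two exploratory composites after NYHA, PGIC and KCCQ assessment has stopped, which slightly understates the event rate

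*SAP*

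**What the plan says.** SAP 6.2.9 first describes how the incidence of deaths, CV hospitalizations and outpatient HF events will be summarized. That paragraph ends with the only censoring rule in the section: "Patients without an event will be censored at their last contact date (the latest date among all known assessments or follow-up dates". The next paragraph lists three composites to be shown as Kaplan-Meier curves for each arm:

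- the first combines only CV death and HF hospitalization;
- the second is "Time to first occurrence of the composite of CV death, HF hospitalization, worsening from baseline in NYHA class, or worsening from baseline in PGIC";
- the third has CV death, HF hospitalization, and "worsening from baseline in NYHA class, or worsening from baseline in KCCQ CSS".

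The last two contain components that need an assessment. For NYHA, SAP 6.2.2 says: "The NYHA class will be completed at baseline and all following visits". SAP 6.2.1 and Protocol Table 9-1 tie KCCQ and PGIC to numbered visits. No remote mode is described for any of the three.

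Contact can outlast visits. For patients unable to attend, Protocol 6.3.1 says that "follow-up of clinical events specified as exploratory endpoints may continue by phone". Table 9-1 footnote b adds that, after premature treatment discontinuation, "vital status will be collected at week 28 by any method (e.g. via telephone call or e-mail" (the footnote continues with an exception for withdrawn consent). Protocol 9.2.10 is broader: "Vital status will be collected for all randomized patients, including those who did not attend the visit or were permanently discontinued, by any method".

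**The concern.** A patient's last contact date can fall well after the last date on which NYHA, PGIC or KCCQ was assessed. For CV death or HF hospitalization this does no harm, because both can be learned by phone. For the other two composites, the interval between the last assessment and the last contact enters the risk set as event-free time, although half of the components could not have been recorded in it.

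Within an arm the error runs one way: unassessed worsening can only be missed. The estimated event rate is too low and the event-free curve too high. If the arms differ in how many patients are followed by phone only, the curves could also separate slightly without any treatment effect.

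**Working it through.** The documents state no event rate for these composites, so there is no planned figure to reproduce. The check has two parts.

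**1. Does the mechanism follow from the text?** Take a patient last seen at week 12 and reached by phone at week 28. Under the stated rule the censoring date is week 28. NYHA, PGIC and KCCQ were last assessed at week 12, so 28 − 12 = 16 weeks count as event-free without any of them. Neither document gives another censoring date for visit-based components.

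**2. How large is the effect?** All inputs are assumptions except the 28-week horizon:

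- H = 10%: CV death or HF hospitalization by week 28.
- C = 30%: visit-based worsening by week 28, varied from 20% to 40%. The plan gives no expected rate, and no threshold for CSS worsening.
- f: share followed by phone only after their last visit, varied from 2% to 20%.
- w: week of last visit, taken as 12 and varied from 6 to 18.
- Constant, independent hazards. Everyone without an event is contacted at week 28, and deaths and hospitalizations are always learned.

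The true composite rate is 1 − (1 − C)(1 − H) = 1 − 0.70 × 0.90 = 37.0%.

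Under the last-contact rule nobody is censored before week 28, so the Kaplan-Meier estimate is the simple proportion apparently event-free. For attenders this is (1 − C)(1 − H). For telephone-only patients it is (1 − C)^(w/28) × (1 − H), because worsening is seen only up to week w. The shortfall in the event rate is therefore

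f × (1 − H) × [(1 − C)^(w/28) − (1 − C)].

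With w = 12: 0.70^(12/28) = 0.858, so the shortfall is f × 0.90 × (0.858 − 0.700) = f × 0.142.

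| Telephone-only share f | Estimated rate | Error (points) |
|---|---|---|
| 2% | 36.7% | −0.3 |
| 5% | 36.3% | −0.7 |
| 10% | 35.6% | −1.4 |
| 20% | 34.2% | −2.8 |

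Over all the ranges above, the error runs from −0.1 points (C = 20%, f = 2%, w = 18) to −5.3 points (C = 40%, f = 20%, w = 6).

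**Between arms.** With no treatment effect, and 5% telephone-only in one arm against 10% in the other (w = 12), the curves differ by 0.05 × 0.142 = 0.7 points at C = 30%, and by 0.9 points at C = 40%.

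**With censoring at the last assessment.** If stopping visits is unrelated to worsening, the estimate returns to 37.0%. If telephone-only patients worsen at twice the rate after week 12 (f = 10%), the true rate is 38.2%. Last-assessment censoring still gives 37.0% and the current rule 35.6%, so the change moves toward the truth without reaching it.

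**The case against.** Several points on the other side carry weight.

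- **Placement.** The censoring sentence closes the paragraph on event incidence, where last contact is the right date. The composites start a new paragraph with no rule of their own. Applying the rule to them is an inference. It remains the natural reading, since no other rule is given, and if it is wrong the plan has no censoring rule for these curves at all.
- **Use.** Protocol 9.4 lists the composites as exploratory. Protocol 10.3.1 and SAP 6.2.9 only present curves, with no test, hazard ratio or alpha. This stands and limits the importance of the point.
- **Number of patients affected.** A reader might infer that stopping drug means stopping visits. The documents say otherwise: Protocol 6.3.1 and 9.2.9 keep all visits and procedures in place after discontinuation, and 9.2.11 and 9.2.12 add two more visits. Phone follow-up is a fallback. Protocol 10.4 treats drop-out as negligible and 11.4 expects few missing data. Any telephone-only share is therefore assumed.
- **Remote assessment is not forbidden.** SAP 4.2 mentions an electronic PRO diary, so a questionnaire completed at home is conceivable. No section provides for one, and remote contact is described only for clinical events and vital status.
- **Person-time.** It is tempting to take the share of unassessed follow-up as the bias. If 5% to 10% of patients stop at week 6, that share is 0.05 × 22/28 = 3.9% to 0.10 × 22/28 = 7.9%. This is not the error in the curve. The formula above with w = 6 and C = 30% gives 1.0 to 2.0 points.
- **Informative dropout.** If patients who miss visits are doing worse, censoring them at their last assessment is itself informative. This is correct: the change reduces the bias but does not guarantee its removal.

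**Conclusion.** The point holds as a minor specification gap. As written, the rule counts time without NYHA, PGIC or KCCQ assessment as event-free in two of the three composites, and so understates their event rate. The likely size is about 0.7 points at 5% telephone-only and 1.4 points at 10%, under the assumed week-12 last visit, 30% worsening and 10% CV death or HF hospitalization. With the low missingness the protocol expects, it could be smaller.

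Three stronger readings are not supported:

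- That the bias favors or disfavors vericiguat. Its direction between arms depends on which arm has more telephone-only follow-up, which the documents do not say.
- That it touches the trial's conclusions. Confirmatory testing covers only KCCQ PLS and 6MWT (SAP 6.2.5).
- That the treatment of non-CV death belongs to the same error. Whether to censor at it or treat it as a competing event is a separate question, not quantified here, and ordinary censoring there would tend to push the event estimate up.

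A related discrepancy affects patients who do attend. Protocol Table 9-1 footnote e limits the questionnaires at visits 10 and 12 to KCCQ and EQ-5D-5L, while SAP 6.2.1 has PGIC collected there too. Under the protocol schedule, an attending patient's PGIC is not assessed between week 24 and week 28, yet the patient remains at risk for PGIC worsening.

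**What to change.** In SAP 6.2.9:

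1. For the two composites with visit-based components, censor patients without an event at the last date on which that composite's own visit-based components were assessed: NYHA and PGIC for one, NYHA and KCCQ CSS for the other. Define the date by component, because the schedules differ: NYHA is assessed at weeks 4 and 8, when PGIC and KCCQ are not listed in the visit descriptions.
2. Count CV deaths and HF hospitalizations in these composites only up to that date, or up to a stated window reaching to the next scheduled assessment, so that events and event-free time share one cut-off.
3. Keep last contact date for death and for the CV death or HF hospitalization composite.
4. Show the last-contact version of the two curves as a sensitivity display, and report by arm how many patients had contact after their last assessment.
5. Reconcile Protocol Table 9-1 footnote e with SAP 6.2.1 on PGIC at visits 10 and 12. This decides whether the PGIC composite can run beyond week 24.

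The cost is a few sentences, one derived date per composite and an extra figure. Slightly less follow-up is used and a few late deaths or hospitalizations may drop out of these two curves. They remain in the incidence tables and in the CV death or HF hospitalization composite. Some bias stays if patients who miss visits worsen faster.
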